7.4.4 Deaths

Deaths that occur during the protocol-specified AE reporting period that are attributed by the investigator solely to progression of disease will be recorded on the "Trial Discontinuation" eCRF and should not be reported as a SAE. All other on- trial deaths, regardless of attribution, will be recorded on an SAE Report and expeditiously reported to the Sponsor.

When recording a serious adverse event with an outcome of death, the event or condition that caused or contributed to the fatal outcome should be recorded as the single medical concept on the SAE report and Adverse Event page of the eCRF. If the cause of death is unknown and cannot be ascertained at the time of reporting, record "Death NOS" on the eCRF Adverse Event page.

7.4.5 Hospitalization, Prolonged Hospitalization, or Surgery

Any AE that results in hospitalization of > 24 hours or prolonged hospitalization should be documented and reported as an SAE unless specifically instructed otherwise in this protocol. There are some hospitalization scenarios that do not require reporting as an SAE when there is no occurrence of an AE. (See *section 7.3*)

CONFIDENTIAL Page 44 of 66

7.4.6 Pre-existing Medical Conditions

A pre-existing medical condition is one that is present at the start of the trial. Such conditions should be recorded on the General Medical History eCRF. A pre-existing medical condition should be recorded as an AE or SAE only if the frequency, severity, or character of the condition worsens during the trial. When recording such events on an SAE Report Form and/or AE eCRF, it is important to convey the concept that the pre-existing condition has changed by including applicable description.

7.4.7 Pregnancy, Abortion, Birth Defects/Congenital Anomalies

Pregnancy, abortion, birth defects, and congenital anomalies are events of special interest. Please refer to pregnancy Section 7.5.1 for specific instructions.

7.4.8 New Cancers

The development of a new primary cancer should be regarded as an AE and will generally meet at least one of the serious criteria. New primary cancers are those that are not the primary reason for the administration of the study treatment and have developed after the inclusion of the patient into the study. They do not include new lesions of the original cancer. Symptoms of metastasis or the new lesions itself should not be reported as an AE/SAE, as they are considered to be disease progression.

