7 ASSESSMENT OF SAFETY

7.1 Adverse Events

7.1.1 Definitions of Adverse Events

Any untoward medical occurrence in a patient or clinical investigation subject administered a pharmaceutical product and which does not necessarily have a causal relationship with this treatment. An adverse event (AE) can therefore be any unfavorable and unintended sign (including an abnormal laboratory finding), symptom, or disease temporally associated with the use of an investigational product, whether or not related to the investigational product.

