7.1.2 Recording of Adverse Events

All adverse events of any patient during the course of the trial will be reported in the electronic Case Record Form (eCRF), and the investigator will give his or her opinion as to the relationship of the adverse event to trial drug treatment (i.e., whether the event is related or unrelated to trial drug administration). If the adverse event is serious, it should be reported immediately to Sponsor. Other untoward events occurring in the framework of a clinical trial are also to be recorded as AEs (i.e., AEs that occur prior to assignment of trial treatment that are related to a protocol-mandated intervention, including invasive procedures such as biopsies, medication washout, or no treatment run-in). All AEs regardless of seriousness or relationship to tenalisib, spanning from the informed consent drug until 30 calendar days after the last dose of study drug are to be recorded in the electronic Case Record Form (eCRF).

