7.2 Adverse Event/Serious Adverse Event Causality Assessment

Causality is assessing the relationship of the trial treatment to the adverse event. For this study, the causality assessment will be categorized as related and not related.

- **Related:** All toxicities should be considered related to tenalisib unless there is a clear alternative explanation.
- **Not related:** If there is no temporal association, or another etiology has been identified as the cause, or the trial treatment cannot be implicated based upon the current information.

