7.3 Serious Adverse Events

7.3.1 Definitions of Serious Adverse Events

The definitions of serious adverse events (SAEs) are given below. The principal investigator is responsible for ensuring that all staff involved in the trial is familiar with the content of this section.

CONFIDENTIAL Page 41 of 66

An SAE or reaction is defined as any untoward medical occurrence that: results in death, is immediately life-threatening, requires at least a 24-hour in-patient hospitalization or prolongation of existing hospitalization, results in persistent or significant disability/incapacity, is a congenital anomaly/birth defect or any important medical event.

Medical and scientific judgment should be exercised in deciding whether expedited reporting is appropriate in other situations, such as important medical events that may not be immediately life-threatening or result in death or hospitalization, but may jeopardize the patient or may require intervention to prevent one of the other outcomes listed in the previous definition. These should also usually be considered serious. Examples of such events are intensive treatment in an emergency room or at home for allergic bronchospasm; blood dyscrasias or convulsions that do not result in hospitalization; or development of drug dependency or drug abuse. *Progression of malignancy (including fatal outcomes)*, if documented by use of appropriate method (for example, as per RECIST version 1.1 criteria), should not be reported as a serious adverse event.

Treatment within or admission to the following facilities is not considered to meet the criteria of "in-patient hospitalization" (although if any other SAE criteria are met, the event must still be treated as an SAE and immediately reported):

- Emergency Department or Emergency Room
- Outpatient or same-day surgery units
- Observation or short stay in unit
- Rehabilitation facility
- Hospice or skilled nursing facility
- Nursing homes, Custodial care or Respite care facility

Hospitalization during the trial for a pre-planned surgical or medical procedure (one which is planned prior to entry in the trial or planned in advance and not related to the study procedure/drug), does not require reporting as a serious adverse event to the Sponsor.

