7.4.9 Lack of Efficacy

When there is deterioration in the condition for which the study treatment is being used, there may be uncertainty as to whether this is lack of efficacy or an AE. In such cases, unless the sponsor or reporting physician considers the study treatment contributed to the deterioration of the condition, the deterioration should be considered lack of efficacy and not an AE.

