New lesion response is classified as present or not ("Yes" or "No"). The response is "Yes" if there is at least one lesion that the investigator considers unequivocal new tumour.

CONFIDENTIAL Page 52 of 66

- Lesions that are equivocal (for example, due to small size) should not be considered new until they are confirmed by later scanning. Once confirmed, they can be retrospectively called new lesions at the time they were first seen.
- A lesion identified in an area not previously scanned is considered a new lesion.
- New lesions seen on nuclear medicine bone scans should be confirmed using anatomical imaging, whenever possible. If bone lesions are confirmed on later CT or MRI scan, progression should be assigned to the visit in which new lesion(s) were first seen on bone scan (in a manner similar to other equivocal new lesions). In the absence of structural confirmation, the pattern of lesions must clearly indicate metastasis, usually with at least two new lesions present.

Overall response is determined by combining the target, non-target, and new lesion responses.

| Table 9 | : | Response | Assessment |
|---------|---|----------|-------------------|
|---------|---|----------|-------------------|

| Target Lesions | Non-Target Lesions | New Lesions | Overall Visit Response |
|-----------------------|---------------------|-------------|---------------------------|
| CR | CR | No | CR |
| CR | Non-CR/Non-PD or NE | No | PR |
| PR | Non-CR/Non-PD or NE | No | PR |
| SD | Non-CR/Non-PD or NE | No | SD |
| PD | Any | Yes or No | PD |
| Any | PD | Yes or No | PD |
| Any | Any | Yes | PD |

After all visits have been evaluated, the sequence of overall visit responses is used to derive best overall response (BOR).

- BOR is defined as the best visit response recorded from the start of the treatment until disease progression/recurrence.
- ORR: It is defined as sum of CR and PR rates
- Clinical Benefit Rates: It is defined as sum of CR, PR and SD rates
- PFS is measured from the time of first dose of study drug to radiographic (or tumour marker as applicable) documentation of disease progression or death due to any cause.

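### Section 7.4.8 keeps symptoms of metastasis off the AE and SAE forms on attribution alone, which conflicts with 7.3.1 and 7.4.9 and can leave symptomatic toxicity unrecorded

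*Protocol*

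**What the plan says.** Section 7.4.8, which separates new primary cancers from lesions of the cancer under study, ends with this rule: "Symptoms of metastasis or the new lesions itself should not be reported as an AE/SAE, as they are considered to be disease progression". It covers AE and SAE reporting alike.

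Five other protocol sections bear on the same event:

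- **7.1.1** defines an AE to include any unfavourable "symptom, or disease temporally associated with the use of an investigational product, whether or not related to the investigational product".
- **7.1.2** sends to the eCRF "All AEs regardless of seriousness or relationship to tenalisib", from consent to 30 days after the last dose.
- **6.3.4** asks that new clinically significant abnormal examination findings after the first dose be entered as AEs.
- **7.3.1** says that progression of malignancy, including a fatal outcome, "if documented by use of appropriate method (for example, as per RECIST version 1.1 criteria), should not be reported as a serious adverse event".
- **7.4.9** says that, where it is unclear whether a deterioration is lack of efficacy or an AE, "the deterioration should be considered lack of efficacy and not an AE", but only "unless the sponsor or reporting physician considers the study treatment contributed to the deterioration of the condition".

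On causality, 7.2 states: "All toxicities should be considered related to tenalisib unless there is a clear alternative explanation". On efficacy, 8.5 states: "PFS is measured from the time of first dose of study drug to radiographic (or tumour marker as applicable) documentation" of progression, or to death from any cause. SAP 8.7.2 censors everyone else at the last date known to be radiologically progression free.

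**The concern.** Under 7.4.8 the investigator's view that a symptom comes from metastasis is enough to keep it off the form. The causality rule in 7.2 works on events treated as toxicities, so an event set aside as metastatic may never have its causality recorded.

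This matters because some harms the protocol says to look for resemble disease at common metastatic sites. Section 3.4.5 names pneumonia/pneumonitis, and lung is one of the metastatic sites in SAP Table 14.1.3.1. Cough or dyspnoea could be read either way.

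AEs, Grade 3/4 AEs and SAEs are a stated secondary endpoint (3.1.2). The trial is meant to pick one of two doses partly on an acceptable safety profile (1.5.2). The medical monitor reviews AEs and SAEs (12.3), and SAP 7.4 plans no other data monitoring. An event that is not entered is missing from the AE tables and may also escape that review.

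**Working it through.** The plan states no figure on this point, so there is none to reproduce. The check compares the texts, then gives a scale.

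**Step 1. Conditions for leaving an event off the forms**

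| Section | What is exempted | From which record | Documentation needed? | Drug-contribution exception? |
|---|---|---|---|---|
| 7.3.1 | Progression, including fatal | SAE | Yes, e.g. RECIST 1.1 | None stated |
| 7.4.4 | Death attributed solely to progression | SAE | No | Implied by solely |
| 7.4.8 | Symptoms of metastasis; new lesions | AE and SAE | No | No |
| 7.4.9 | Uncertain deterioration | AE | No | Yes |

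Only 7.4.8 lacks both safeguards, and it has the widest reach. For new lesions the gap is nominal, because an unequivocal new lesion is itself progression under 8.5 and Table 9. The gap lies in the symptoms.

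**Step 2. A test case.** Take a serious symptom attributed to metastasis, with no documented progression. It does not meet the condition in 7.3.1, so that exemption does not apply and it is reportable as an SAE. Section 7.4.8 says not to report it. Both instructions cannot be followed.

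**Step 3. Effect on efficacy records**

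- Primary endpoint: SAP Table 14.2.1.1 counts patients with at least 180 days of treatment, over all N in the group. A patient who stops earlier stays in N as a non-success.
- PFS: 8.1 lists suspected clinical progression as a reason to scan. Section 6.8 waives the end-of-treatment scan if one was done within 28 days. If no scan or marker documents progression and the patient is alive, she is censored.

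**Step 4. Scale.** With 20 patients per group, one patient is 1/20 = 5 percentage points.

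- 2/20 = 10%, exact 95% CI 1.2% to 31.7%
- 1/20 = 5%, exact 95% CI 0.1% to 24.9%

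Let p be the true rate of a toxicity and m the share read as disease. The documents give neither, so both are assumptions. The chance that a group of 20 records at least one case is 1 − (1 − p(1 − m))^20:

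| p | m = 0 | m = 25% | m = 50% |
|---|---|---|---|
| 5% | 0.642 | 0.534 | 0.397 |
| 10% | 0.878 | 0.790 | 0.642 |
| 15% | 0.961 | 0.908 | 0.790 |

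For example, at p = 10% and m = 50%: 1 − 0.95^20 = 0.642.

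**The case against.** The strongest reply is that 7.4.8 is a specific exception to the general rule in 7.1.2, and that calling something a symptom of metastasis presupposes the cause is known. Uncertain cases would then go to 7.4.9, with its drug exception. This is a fair reading for 7.1.2, although neither section says so. It does not settle the conflict with 7.3.1, which is equally specific and sets a condition that 7.4.8 omits.

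Several safeguards do stand, and they limit the point:

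- **Laboratory toxicity.** A reader might infer that a liver-enzyme signal could be lost. The documents do not support this. Section 7.4.3 makes Grade 3/4 laboratory abnormalities AEs, and SAP 8.8.3 summarises ALT, AST, bilirubin, ALP and GGT and lists abnormal values. The protection is not complete: 7.4.3 lets an associated sign, symptom or diagnosis stand in for the value on the AE form. The laboratory data remain even then.
- **Recovery.** A reader might infer that an omitted event is gone for good. Traces can remain in abnormal examination findings, reasons for changes to study drug, reasons for medication and reasons for discontinuation, all of which the SAP lists. They would not appear in the AE tables.
- **Direction.** Attribution is made with dose known, but both arms receive tenalisib and no inferential AE comparison is planned. Nothing shows that the omission would favour one dose.
- **Reporting policy.** Keeping disease outcomes out of AE reporting is a legitimate choice, made in several sections. Recording every disease symptom as an AE would be a debatable change and is not needed here.

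**Conclusion.** The point holds as an inconsistency with a limited consequence. Section 7.4.8 excludes symptoms of metastasis on attribution alone, against the documentation condition in 7.3.1, the drug-contribution exception in 7.4.9 and the recording duties in 7.1.2 and 6.3.4. What is at risk is symptomatic, non-laboratory toxicity in the AE endpoint, at 5 percentage points per affected patient in an arm of 20. The number affected is unknown, and the probabilities above illustrate assumed rates only.

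A reader might go further and infer that toxicity disappears from both the safety and the efficacy data. That is not supported. The primary endpoint is unaffected under the Table 14.2.1.1 rule, and death always counts for PFS. If scans show no progression, recording no progression event is what the PFS definition requires. The remaining efficacy effect is a patient with clinical progression that no scan documents, who is censored for PFS.

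**What to change.** Reconcile 7.4.8 with 7.3.1 and 7.4.9, and check 7.4.4, which also rests on attribution:

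1. Limit the 7.4.8 exemption to progression or new lesions documented as 7.3.1 requires.
2. Do not apply it where a drug contribution is considered possible, as in 7.4.9.
3. In all other cases, record the symptom as an AE or SAE and assess causality under 7.2. The related and not related columns of SAP Table 14.3.1.2 already separate these events.

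The cost is protocol wording and a few more AE records. The downside is that all-causality counts will include some disease symptoms.

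SAP 5.1 reports that the study closed early, so new wording may come too late for data collection. If the database is still open, the sponsor can check source records for patients stopped for progression without documented PD. The study report should in any case state the rule that was applied.

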7.4.9 Lack of Efficacy

When there is deterioration in the condition for which the study treatment is being used, there may be uncertainty as to whether this is lack of efficacy or an AE. In such cases, unless the sponsor or reporting physician considers the study treatment contributed to the deterioration of the condition, the deterioration should be considered lack of efficacy and not an AE.

7.5 Protocol-Defined Events of Special Interest

The following are events of special interest and will need to be reported expeditiously.

7.5.1 Pregnancy, Abortion, Birth defects/Congenital anomalies

Female patients who are not of child-bearing potential (see Appendix B) and female patients of child-bearing potential who have a negative pregnancy test within 72 hours prior to C1D1 are eligible for the study. Female patients of child-bearing potential (see Appendix B)) must consent to use a medically acceptable method of contraception throughout the study period and for 30 days after the last dose of tenalisib.

During the course of the trial, all female patients of childbearing potential must contact the treating investigator immediately if they suspect that they may be pregnant (a missed or late menstrual period should be reported to the treating investigator).

If an investigator suspects that a patient may be pregnant prior to administration of trial drug(s), the trial drug(s) must be withheld until the result of the pregnancy test is confirmed. If a pregnancy is confirmed, the patient must not receive any trial drug(s) and must be discontinued from the trial. The outcome of the pregnancy will be monitored as outlined in *Appendix B*.

CONFIDENTIAL Page 45 of 66

If an investigator suspects that a patient may be pregnant after the patient has been receiving trial drug(s), the trial drug(s) must immediately be withheld until the result of the pregnancy test is confirmed. If a pregnancy is confirmed, the trial drug(s) must be immediately and permanently stopped, the patient must be discontinued from the trial, and the investigator must notify the Medical Monitor and Sponsor Representative as soon as possible. If a patient becomes pregnant while enrolled in the trial, a Pregnancy Form should be completed and faxed to the Sponsor. The outcome of the pregnancy will be monitored as outlined in *Appendix B*.

Congenital anomalies/birth defects always meet SAE criteria, and should therefore be expeditiously reported as an SAE, using the previously described process for SAE reporting. A Pregnancy Form should also have been previously completed and will need to be updated to reflect the outcome of the pregnancy.

7.5.2 Overdose

An overdose is defined as accidental or intentional administration of any dose of product that is considered both excessive and medically important. For purposes of this trial, an overdose will be defined as any dose exceeding the proposed dose of tenalisib (i.e 1200 mg BID).

Symptomatic and non-symptomatic overdose must be reported in the eCRF. Any accidental or intentional overdose with the trial treatment that is symptomatic, but not fulfilling a seriousness criterion, is to be reported to the Sponsor immediately as an AE. All symptomatic overdose, fulfilling a seriousness criterion, is to be reported as an SAE as per the SAE reporting procedure. For patients who experience overdose, treatment should consist of supportive therapy. A decision to interrupt treatment or dose reduction to be taken depending on the symptoms.

7.6 Dose Modifications

In case of hematologic and non-hematologic toxicities, the dose modifications provided below (**Table 6** and **Table 7**) should be used as a guidance and should be determined as per PI's clinical judgement. The dose modifications are intended to be applied when the investigator determines the events related to tenalisib. If events (cytopenia) are deemed related to the underlying disease rather than tenalisib, dose reduction will be done as per the investigator's discretion. In case of drug withhold, tenalisib treatment can be resumed if:

- Patient recovers from grade 3-4 toxicity as defined in dose modification guidance below.
- No clinical or radiographic evidence of disease progression.
- Investigator believes the risk of progression outweighs the risk of further treatment.

If treatment is delayed >2 weeks, treatment continuation should be discussed with Medical monitor. The treatment should be permanently discontinued if withhold of study drug due to drug related toxicity is for > 28-days unless approved by medical monitor.

At the discretion of the investigator, a dose re-escalation may be permitted for patients who earlier has dose reduction. The decision should be taken after evaluating the emerging safety data and benefit and risk of re-escalation. Drug holidays are discouraged. Any patient in whom similar toxicity recurs at the reduced dose, it should be discussed with medical monitor to determine appropriate strategy on treatment continuation.

CONFIDENTIAL Page 46 of 66

Table 6: Dose modifications for hematologic toxicity

| CTCAE Grade | Action to be Taken |
|--|---|
| Hematologic toxicity | |
| Grade 3 Neutropenia $(1.0 \times 10^9/L < ANC \ge 0.5 \times 10^9/L)$ | Maintain dose level.Monitor ANC at least weekly. |
| Grade 4 Neutropenia (0.5 x 10 ⁹ /L <anc)< th=""> First incidence: Hold dose until resolved to ≤ Grade 2 or baseline. Monitor ANC at least weekly. Resume treatment at the same dose level. Subsequent occurrence: Hold dose until resolved to ≤ Grade 2 or baseline, consider growth factor support. Resume treatment at one dose lower* if warranted. Discontinue if further dose modification required at lowest dose. 	</anc)<> | First incidence: Hold dose until resolved to ≤ Grade 2 or baseline. Monitor ANC at least weekly. Resume treatment at the same dose level. Subsequent occurrence: Hold dose until resolved to ≤ Grade 2 or baseline, consider growth factor support. Resume treatment at one dose lower* if warranted. Discontinue if further dose modification required at lowest dose. |
| Grade 3 Febrile neutropenia ANC <1.0 X 10^9 /L with a single temperature of > 38.3^0 C (101^0 F) or a sustained temperature of $\ge 38^0$ C (100.4^0 F) for more than one hour. | Withhold dose until resolved to ≤ Grade 2 or baseline, consider growth factor support, then reduce by 1 dose level*, if warranted. If the ANC is <1 X 10⁹/L (1000/μL) before therapy, the dose shall not be modified as long as ANC >0.5 X 10⁹/L. |
| Grade 3 Thrombocytopenia $(50.0 \times 10^9 / L < PLT \ge 25.0 \times 10^9 / L)$ with Grade 1 bleeding | Maintain dose level.Monitor platelet count at least weekly. |
| Grade 4 thrombocytopenia (20.0 X 10 ⁹ /L< PLT) OR Grade 3 thrombocytopenia with Grade 2 bleeding | 1st occurrence: Hold dose until to ≤ Grade 2 or baseline or resolution of bleeding. Consider platelet transfusion as necessary. Resume treatment at the same dose level. Subsequent Occurrences: Hold dose until to ≤ Grade 2 or baseline or resolution of bleeding. Consider platelet transfusion as necessary. Resume treatment at one dose lower* if warranted. Discontinue if further dose modification required at lowest dose*. |

Note: The drug interruption and dose modification should be discussed with medical monitor.

CONFIDENTIAL Page 47 of 66

^{*}See 'Guidelines for dose reduction' below.

Table 7: Dose modifications for non-hematologic toxicity

| | eations for non-hematologic toxicity |
|--------------------------|--|
| Non-Hematologic Toxicity | |
| Infection | Grade 3 or higher sepsis or pneumonia |
| | Withhold tenalisib until infection has resolved. |
| | • Restart at the same or at the reduced dose level*, if warranted. |
| Skin rash (Cutaneous | Grade 1-2 |
| reactions) | • Maintain tenalisib dose. Initiate supportive care with emollients, |
| | antihistamines (for pruritus), or topical steroids |
| | Monitor closely until resolved. |
| | Grade 3 |
| | • Withhold tenalisib dose. Initiate supportive care with emollients, |
| | antihistamines (for pruritus), or topical steroids |
| | Monitor at least weekly until resolved. |
| | • Restart tenalisib at the reduced dose level*. |
| | • If severe cutaneous reaction does not improve, worsens, or |
| | recurs, discontinue tenalisib. |
| | Life threatening or SJS, TEN, DRESS (any grade) |
| | Discontinue tenalisib permanently. |
| Pneumonitis without | Moderate (Grade 2) symptomatic pneumonitis |
| suspected infectious | • Withhold tenalisib dose. Initiate systemic steroid therapy. If |
| cause | pneumonitis recovers to Grade 0 or 1, tenalisib may be resumed |
| | at reduced dose*. |
| | • If non-infectious pneumonitis recurs or patient does not respond |
| | to steroid therapy, discontinue tenalisib. |
| | Severe (Grade 3) or life-threatening pneumonitis |
| | Discontinue tenalisib. Treat with systemic steroid therapy. |
| Non-infectious Diarrhea | Moderate diarrhea, responsive to antidiarrheal agents: |
| | Maintain tenalisib dose. Monitor at least weekly until resolved. |
| | Moderate diarrhea, unresponsive to antidiarrheal agents: |
| | • Withhold tenalisib dose. Initiate supportive therapy with enteric |
| | acting steroids (e.g., budesonide). |
| | Monitor at least weekly until resolved. |
| | • Restart tenalisib at the reduced dose level*. |
| | Severe diarrhea or hospitalization: |
| | • Withhold tenalisib dose. Initiate supportive therapy with enteric |
| | acting steroids (e.g., budesonide) or systemic steroids. |
| | Monitor at least weekly until resolved. |
| | • Restart tenalisib at the reduced dose level*. |
| | Life threatening diarrhea: |
| | Discontinue tenalisib permanently. |
| Hepatic* | Transaminitis |
| | Grade 1-2 Transaminitis (ALT/AST >1-3 x ULN if baseline is |
| | normal; 1.5 -3 x baseline if baseline is abnormal): |

CONFIDENTIAL Page 48 of 66

| | Maintain tenalisib dose and initiate prednisone 40 mg daily. | | | |
|--------------------------|--|--|--|--|
| | Monitor AST/ALT weekly until resolved and then taper steroid. | | | |
| | • Withhold tenalisib in case of development of grade 2 | | | |
| | transaminitis or worsening of Grade 1 transaminitis while on | | | |
| | steroids. | | | |
| | Grade 3 Transaminitis (ALT/AST >5–20 x ULN; >5-20 x | | | |
| | baseline if baseline is abnormal): | | | |
| | Withhold tenalisib and monitor ALT/AST twice a weekly until | | | |
| | Grade ≤1; restart tenalisib at one dose lower*. | | | |
| | Initiate prednisone 1 mg/kg in case no improvement after | | | |
| | withholding tenalisib for 1 week. | | | |
| | • Monitor ALT/AST twice a weekly until Grade ≤1; restart | | | |
| | tenalisib at one dose lower* and taper steroid. | | | |
| | • If no immediate response to steroids within 7 days, initiate | | | |
| | mycophenolate mofetil. | | | |
| | • Discontinue if further dose modification required at lowest dose. | | | |
| | Grade 4 Transaminitis (ALT/AST >20 x ULN; >20x baseline if | | | |
| | baseline is abnormal): | | | |
| | Tenalisib should be permanently discontinued. | | | |
| | Bilirubin: | | | |
| | Grade 2 (> 1.5-3 x ULN; >1.5-3 x baseline if baseline is abnormal): | | | |
| | • Maintain tenalisib dose. Monitor at least weekly until ≤ 1x | | | |
| | ULN. | | | |
| | Grade 3 (> 3 -10 x ULN; > 3 -10 x baseline if baseline is abnormal): | | | |
| | • Withhold tenalisib. Monitor at least weekly until bilirubin is ≤ | | | |
| | 1x ULN. | | | |
| | • Restart tenalisib at one dose lower*. | | | |
| | Grade 4 (> 10 x ULN; >10 x baseline if baseline is abnormal): | | | |
| | Discontinue tenalisib permanently. | | | |
| Other non-hematologic to | xicities | | | |
| Grade 1 or 2 | None | | | |
| Grade 3 | Withhold tenalisib dose until toxicity Grade ≤2. Restart tenalisib at | | | |
| | one dose lower* if warranted. | | | |
| Recurrence of grade 3 | Withhold tenalisib dose until toxicity Grade ≤2; Restart tenalisib at | | | |
| toxicity | one dose lower* or discontinue treatment. | | | |
| Grade 4 | Withhold tenalisib dose until toxicity Grade ≤2; Restart tenalisib at | | | |
| | one dose lower* or discontinue tenalisib. | | | |
| Recurrence of grade 4 | Discontinue tenalisib | | | |

toxicity

*See 'Guidelines for dose reduction' below.

Note: The drug interruption and dose modification should be discussed with medical monitor.

Page 49 of 66 CONFIDENTIAL

| Table 6. Guidance on Tenansio Dose reduction | | | | | | |
|--|--------------------|--------------------------------|--------------------------------|--|--|--|
| Group | 1st Dose reduction | 2 nd Dose reduction | 3 rd Dose reduction | | | |
| Group 1 (Tenalisib 800 mg BID) | 400 mg BID | Discontinue | - | | | |
| Group 2 (Tenalisib 1200 mg BID) | 800 mg BID | 400 mg BID | Discontinue | | | |

Table 8: Guidance on Tenalisib Dose reduction

